#### 3. Abstract:

Although compelling evidence exists that high doses of mother's own breast milk (mother's own milk; MOM) improves infant health, breast pump dependent (need to use a breast pump to obtain milk for infants too ill or preterm to breastfeed) mothers of critically ill infants often provide insufficient amounts of MOM to support these benefits. Insufficient MOM has its origins during the first 14 days postpartum, a critical window that includes secretory activation (SA; milk coming in; lactogenesis II) and the achievement of coming to volume (CTV; providing ≥ 500 mLs/day of MOM by day 14 postpartum). For all lactating mothers, SA must be achieved for lactation to continue, and achievement of CTV predicts provision of MOM through to neonatal intensive care unit (NICU) discharge in preterm very low birthweight (VLBW; <1500 g birthweight) infants. For this study, we posit that alternate breast pump suction patterns (BPSP; suction rate, intensity, and rhythm) may facilitate achievement of CTV in mothers who have achieved SA, but whose daily pumped MOM volumes indicate a high risk of not achieving CTV. Therefore, the overall objective of this study is to compare the clinical effectiveness of three different breast pump suction patterns on lactation outcomes, including achievement of SA, among pump dependent mothers of critically ill infants who demonstrate faltering lactation after achievement of SA. At 6-8 days postpartum, 90 pump dependent mothers of critically ill infants who have achieved SA, but demonstrate faltering lactation (<350 mLs/day pumped MOM volume), will be randomized to use one of three different BPSPs with two groups having alternative BPSPs and one group using the current practice standard for 7 days. Study outcomes will include the following; (1) pumped milk volume, (2) secondary lactation outcomes (whether or not mothers achieve CTV by day 14-15 postpartum, maintenance of secretory activation, MOM removal efficiency, and lactation duration); (3) maternal perceptions of comfort, effectiveness, efficiency, and convenience of the BPSPs, and (4) proportion of feedings consisting of MOM consumed by infants. Two exploratory aims will explore potential benefits of the 3 BPSPs on lactation outcomes of mothers with co-morbidities known to negatively affect the above-mentioned lactation outcomes and whether mothers at risk of suboptimal lactation who use an alternate BPSP achieve the same lactation outcomes as do mothers who do not demonstrate faltering lactation.

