## Specific aims are as follows:

**Aim 1**: Compare the clinical effectiveness of 3 different BPSPs on pumped milk volume during Days 8-15 postpartum.

**Aim 2:** Compare lactation outcomes for the three groups, including 1) maintenance of SA through to postpartum day 14-15, 2) rate of increase in daily pumped MOM volume, 3) whether or not mothers achieve CTV by day 14-15 postpartum, 4) cumulative pumped MOM volume over days 1-7 and 8-15) MOM removal efficiency, and 5) lactation duration.

Aim 3: Compare maternal perceptions of comfort, effectiveness, efficiency, and convenience of the 3 BPSPs.

**Aim 4:** Compare infant outcomes for the including: 1) proportion of feedings consisting of MOM during the NICU hospitalization, 2) proportion discharged consuming any MOM, and 3) proportion receiving MOM at 3 and 6 months of life.

**Exploratory Aim 1**: Explore potential benefits of the 3 BPSP on lactation outcomes of mothers with comorbidities known to negatively affect lactation outcomes (high BMI/obesity, diabetes, pregnancy induced hypertension).

**Exploratory Aim 2**: Explore whether mothers categorized as having faltering lactation on postpartum day 6-8 and who use BPSP1, BPSP2, or Symphony Plus BPSP (Standard Care) achieve the same lactation outcomes (Aims 1, 2, 4) as do mothers who do not demonstrate faltering lactation at postpartum day 6-8.

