The NICU at UF Shands admits infants that are racially diverse regardless of private or Medicaid insurance coverage. All mom that meets the above criteria would be eligible for enrollment. Informed consent will be obtained by mothers in their postpartum hospital room or in the NICU while visiting their infant prior to 48 hours postpartum. The informed consent includes mother's permission to access their infant's chart to collect information up until infant's discharge. The infant has no study interventions. In the rare instance that an infant breastfeeds, intake will be determined through test weighting (infant weight pre and post breastfeeding). Prior to the mother's hospital discharge, she will be provided an empty payment card where participants will receive compensation, by adding payments for completing study events, listed below. After enrollment, a 2-minute maternal interview will be used to collect information to determine pre-pregnancy BMI and other factors that might impact lactation success (Appendix B). Information will be collected related to pumping frequency and pumped milk volume prior to enrollment (Appendix I). All enrolled mothers will be provided breast pumping instructions to optimize their pumping behaviors prior to achievement of secretory activation. This 30-minute optimization session will be provided by a Research Nurse Coordinators, who is also an International Board-Certified Lactation Consultant (IBCLC). The instructions will be standardized using a score card, which provides prompts for education discussion and video links about pumping practices, breast and nipple assessment, breast shield sizing and comfort. (Appendix F). A daily sample of 0.3 mL of pumped MOM (if mother has pumped at least 5mL/day) will be tested for MOM sodium level as an indicator of secretory activation. At day 6-8 postpartum, mothers at high risk of suboptimal lactation will be identified and randomized to one of three BPSPs Mothers will be determined to be at risk if they have (1) achieved secretory activation (change from small volumes of colostrum to large volumes of more mature milk; determined by a milk sodium level < 20 mM) and (2) have a pumped milk volume < 350 mL/d. Mothers who are identified as being not at risk for suboptimal lactation (have achieved secretory activation and their pumped milk volume is > 350mL/d) will not be randomized but will continue with standard care regarding BPSPs, and continue to have data regarding lactation collected. Mothers who do not reach SA, determined by a milk sodium level > 20 mM, will be withdrawn from the study and referred to the UF Shands Lactation Team. All mothers that achieve SA, will be provided a second 30-minute standardized breast pumping optimization session with instructions by a Research Nurse Coordinator who is an IBCLCs at day 6-8 postpartum. Mothers will complete the Maternal Perceptions Survey (Appendix K/Part A only) before starting new pattern. If randomized, Moms will complete the Maternal Perception Survey (Part A/B) on Day 9-11. A score card, designed for mothers who have already achieved secretory activation, includes educational prompts and video links regarding milk volume, pumping behaviors, breast and nipple assessment, flange fit and comfort will be utilized. (Appendix G). Should a mother be unable to obtain transportation to the NICU, they will be provided transportation through Uber Health, provided they live within a 60-mile radius of UF Shands due to cost limitation of study.

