**Aim 3:** Will compare maternal perceptions of comfort, effectiveness, efficiency, and convenience of the 3 different breast pump patterns.

Mother's perception regarding the comfort, rhythm, effectiveness, and ease of use of the three BPSPs will be assessed via a text message hyperlinked Qualtrics survey within 7 days of study completion. A reminder will be sent if no response in 7 days (Appendix K).

**Aim 4:** A fourth aim will compare proportion of feedings consisting of MOM consumed by infants between the 3 groups. Daily proportion of total feeds consisting of MOM consumed during the first 15 days and proportion of total feeds consisting of MOM consumed during the 24 hours prior to discharge will be recorded from the infant's EMR. Proportion of feeds that include MOM after discharge will be determined until the mother ceases lactation or the infant is 6 months old through monthly text message hyperlinked surveys through Qualtrics asking the total number of feeds in the past 24-hours that consisted of MOM (either direct breastfeeding or feeding expressed MOM).

**Exploratory Aim 1**: Will explore potential benefits of the three BPSPs on the lactation outcomes in Aim 1 and 2 of mothers with co-morbidities known to negatively affect lactation outcomes (high BMI/obesity, diabetes, pregnancy induced hypertension).  A subset of mothers diagnosed with high BMI/obesity, diabetes, and/or pregnancy induced hypertension will be classified as having 1, 2, or 3 risk factors known to negatively affect lactation outcomes. Potential benefits of the three BPSPs will be explored in this subset of mothers.

Exploratory Aim 2: Explore whether mothers identified as having faltering lactation who use an alternate BPSP (BPSP 1 or 2) achieve the same lactation success as mothers identified as not having faltering lactation (pumped MOM volume  $\geq 350$  mL/d by day 6-8). Lactation outcomes (see Aim 1 and 2) will be compared between mothers who were randomized to use either BPSP 1 or 2 and those mothers who were not randomized because they were not identified as having faltering lactation.

Confounding Variables. The following variables may affect pumped MOM volume in mothers of critically ill infants. While control of these variables within the study is impossible, we will carefully document these factors on all enrolled mothers to allow for inclusion in statistical analysis as adjustment variables. See **Table 1** for additional confounding variables.

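### Exploratory Aim 2 is stated in incompatible ways, and the version in the procedures leaves out the standard-care arm needed to interpret any catch-up

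*Protocol*

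**What the plan says.** Three places in the protocol define Exploratory Aim 2.

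- Section 5 (Specific Aims) asks about faltering mothers "who use BPSP1, BPSP2, or Symphony Plus BPSP (Standard Care) achieve the same lactation outcomes (Aims 1, 2, 4" as mothers without faltering lactation.
- Section 6 (Research Procedures and Analyses by Specific Aim) asks whether "mothers identified as having faltering lactation who use an alternate BPSP (BPSP 1 or 2) achieve the same lactation success" as the non-faltering mothers. It then sets the analysis: "Lactation outcomes (see Aim 1 and 2) will be compared between mothers". The two sides are named in the same sentence, the outcomes being "compared between mothers who were randomized to use either BPSP 1 or 2 and those mothers who were not randomized".
- Section 3 (Abstract) refers to whether "mothers at risk of suboptimal lactation who use an alternate BPSP achieve the same lactation outcomes" as non-faltering mothers. It does not list outcomes by aim.

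The groups are formed under Sample and Setting in section 6. Mothers are randomised if they have reached secretory activation and "have a pumped milk volume < 350 mL/d" at day 6-8. Mothers above that volume "will not be randomized but will continue with standard care regarding BPSPs". At the same time point, "All mothers that achieve SA, will be provided a second 30-minute standardized breast pumping optimization session". Under Aim 1, randomised mothers, and only they, receive a SMART pump in place of the standard one, with another at the NICU bedside.

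**The concern.** An analyst cannot follow both section 5 and section 6, since they differ on arms and on outcomes. This is not detail left to a statistical analysis plan, because the protocol itself fixes the comparison in two ways.

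The choice affects what the result can mean. The two sides of the section 6 comparison are formed by splitting mothers on their own milk volume, and volume is then the main outcome. Some narrowing of the gap can be expected whether or not a new suction pattern works. The Symphony Plus arm shares the selection rule, the optimisation session and the SMART pump with the BPSP 1 and 2 arms, and differs from them only in pattern. It is the group that shows how much catch-up occurs without a new pattern, and the procedures leave it out of this aim.

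**Working it through.** **The plan's own figure.** No sample size or power is stated for Exploratory Aim 2. The only such figure is for the pairwise comparison of randomised groups: 30 per group, two-sided alpha 0.02, effect size 0.84, 80% power. A two-sample t-test calculation gives 80.25%, so it reproduces, but it does not bear on this aim.

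**The three statements side by side.**

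| Place | Faltering arms compared | Outcomes |
|---|---|---|
| Section 5, Specific Aims | BPSP1, BPSP2, Symphony Plus | Aims 1, 2 and 4 |
| Section 6, procedures | BPSP 1 or 2 | Aims 1 and 2 |
| Section 3, Abstract | an alternate pattern | not listed by aim |

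The abstract agrees with section 6 on arms, so the narrower version is a real candidate for what would be carried out.

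**What can close the gap with no pattern effect.**

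1. *Regression to the mean.* Let r be the correlation between qualifying and later volume, and k the ratio of the later SD to the qualifying SD. With linear regression of later on qualifying volume and no pattern effect:

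   later gap = r × k × gap at selection

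   fraction closed = 1 − r × k

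   The protocol gives neither r nor k. With assumed values:
   - r = 0.5, k = 1: 1 − 0.5 = 50% closed
   - r = 0.9, k = 1: 1 − 0.9 = 10% closed
   - r = 0.8, k = 1.25: 1 − 1.00 = 0% closed

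   If k exceeds 1/r, the gap widens. The amount therefore depends on two quantities that the protocol does not state.
2. *Natural recovery.* Section 4 describes the first 14 days as a period of rapid biological change. A rise shared by both groups leaves the gap alone, but mothers who are merely late would narrow it.
3. *The second optimisation session.* Mothers on both sides receive it, so it closes the gap only if low-volume mothers gain more from it.
4. *The SMART pump.* Only randomised mothers have it. The protocol describes it as the standard pump adapted to record use and weight, so its own effect may be small, but it is a difference between the two sides.

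**What the Symphony Plus arm adds.** Write NF for the non-faltering mean and SP for the Symphony Plus mean. The excess catch-up of a pattern is

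(BPSP − NF) − (SP − NF) = BPSP − SP.

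The non-faltering group cancels. On mean volume, the part that can be assigned to a pattern is the randomised contrast already planned in Aim 1. The comparison with non-faltering mothers describes the remaining gap and carries no further information on the pattern effect.

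**Which outcomes exist on both sides.** Daily volume does, because milk brought to the NICU is weighed for all mothers. Milk removal efficiency does not, because pumping minutes come from the SMART pump.

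**The case against.** The strongest reply is that little is lost. Aims 1 and 2 compare all three randomised arms on volume over days 8-15, rate of increase and coming to volume, so the standard-care trajectory is measured and reported elsewhere. A reader might infer that nothing in the trial shows recovery without a new pattern. The documents do not support that, because the arm is missing only from one exploratory paragraph.

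A reader might also infer that catch-up would be credited to the new patterns. No passage says so. Section 6 asks whether the same success is reached, which can be read as a descriptive benchmark. What stands is narrower: within that comparison, the explanations cannot be separated.

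Third, it is tempting to put the untreated closing in mL/d and set it beside the 300 mL design difference. That would need an assumed correlation, an assumption of equal SDs over time, and the planning SD of 350 reused for all mothers before selection. A normal distribution with mean 350 and SD 350 puts about 16% of volumes below zero, and the protocol's 300 mL carries no per-day unit. Nor does the text say that a single reading decides eligibility; averaging several days would raise r and shrink the effect.

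These points limit the weight of the concern. They do not remove the conflict between sections 3, 5 and 6, or the weakness of the narrower version.

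**Conclusion.** The inconsistency is certain: section 5 names three arms and Aims 1, 2 and 4; section 6 names two arms and Aims 1 and 2; the abstract follows section 6 on arms. If section 6 is followed, catch-up by the BPSP 1 and 2 mothers could not be distinguished, within that comparison, from regression to the mean, natural recovery or the co-interventions.

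No size can be given from the protocol. The 0% to 50% closing shown above only illustrates how far the answer moves with assumed inputs. The aim is exploratory and the randomised comparisons of Aims 1 and 2 are unaffected, so this concerns consistency and interpretation and does not threaten the primary result. It is still worth correcting: a finding that faltering mothers on a new pattern matched non-faltering mothers is easy to over-read, and the arm that guards against this is already randomised and measured.

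**What to change.** - Align the wording of Exploratory Aim 2 in section 3 and in the section 6 procedures with section 5: all three randomised arms, outcomes of Aims 1, 2 and 4.
- Report BPSP1, BPSP2 and Symphony Plus each against the non-faltering mothers, with 95% confidence intervals, on the outcomes measured in both groups. Base volume on the NICU weighing that covers all mothers, and exclude milk removal efficiency.
- State that any effect of a pattern is judged from the randomised contrast with Symphony Plus, and not from catch-up to the non-faltering group.

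The cost is wording in two places, one added sentence and one more group in an exploratory table. No new data are needed.

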3. Duration of partial or exclusive MOM feedings after discharge	Monthly maternal text message with hyperlinked surveys through Qualtrics. (App J)	Monthly until lactation cessation or infant is 6 months of age.					
Length of NICU hospital stay; infant nutritional, and health outcomes	Days infant remained hospitalized in the NICU, nutritional and health outcomes	From birth until discharge.					
Covariates (1-6) below							
1. Demographic data	Maternal: Race/Ethnicity, delivery of > one infant, delivery mode, parity, BMI, co-morbidities. Infant : Gestational age at birth, birthweight, Apgar score. % of type of feeding consumed (MOM, donor human milk, formula). (App A, App N)	Upon entry into study and during the 15-day study period					
2. Number of pumping sessions per day	# of times a mother pumps her breasts per day. (App L)	Daily for 15 days					
3. Skin-to-skin care	Total minutes and episodes of skin-to-skin care.	Daily for 15 days.					

4. Maternal mood	Results of 2 MAACL-R tests completed by mom.	Prior to her hospital discharge and at 15					
	(App D)	days postpartum.					
5. Lactation experience	(a) Feeding plan prior to delivery, previous experience	Before maternal hospital discharge (a)					
	with breastfeeding and/or pumping, lactation intent, home	At end of study (b)					
	pump status (b) Lactation intent, lactation goals lactation						
	consultations, galactagogues, mastitis diagnosis and						
	treatment, use of hormonal birth control, home pump status						
	(App C)						

Table 2: Timeline of events over the 15-day study

Measure	0*	1	2	3	4	5	6	7	8	9	10	11	12	13	14	15
Consent, maternal interview		Х-	-X													
Pumping optimization		X-		-X			X-		-X							
MOM NA/K Level		Х-														- X
Lactation risk assessment							X-		-X							
Randomization							X-		-X							
Determination of CTV																X
Measures of pumped milk volume		X	X	X	X	X	X	X	X	X	X	X	X	X	X	X
Measures of infant consumption of MOM		X	X	X	X	X	X	X	X	X	X	X	X	X	X	X
Maternal perception survey (Part A)							Х-		-X							
Maternal perception survey (Part A/B)										Х-		-X				
MACCL			Х-	-X												X
Lactation experiences			X													X

\* = day of birth

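### The candidate adjustment variables include factors measured after randomisation, and one of them is itself an Aim 4 outcome

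*Protocol*

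**What the plan says.** The protocol fixes the time of allocation under Sample and Setting: "At day 6-8 postpartum, mothers at high risk of suboptimal lactation will be identified and randomized to one of three BPSPs". The allocated pattern is used for 7 days, and the primary comparison is of pumped volume over days 8-15 (Aim 1).

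The Confounding Variables paragraph, at the end of the procedures by aim, lists factors that may affect pumped volume. It says "we will carefully document these factors on all enrolled mothers to allow for inclusion in statistical analysis as adjustment variables", and refers to Table 1 for more. The text then describes skin-to-skin care, lactation support and maternal mood. The Covariates block of Table 1 adds or repeats:

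- the percentage "of type of feeding consumed (MOM, donor human milk, formula"), in a row timed "Upon entry into study and during the 15-day study period";
- the number "of times a mother pumps her breasts per day. (App L"), daily for 15 days;
- "Total minutes and episodes of skin-to-skin care", daily for 15 days;
- "Results of 2 MAACL-R tests completed by mom", the first before maternal discharge and the second at day 15;
- lactation experience, part (a) before maternal discharge and part (b) "At end of study (b"). Part (b) covers intent, goals, consultations, galactagogues and mastitis, among other items.

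Aim 4 compares the daily share of feeds that are MOM over the first 15 days.

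**The concern.** In a randomised comparison, adjusting for characteristics fixed before allocation is safe and usually gains precision. Adjusting for something measured after allocation is different. If the allocated pattern changes it, the adjusted contrast drops the part of the effect that runs through it, and can pick up bias from any unmeasured common cause of that factor and milk volume. The stated purpose is to compare the effectiveness of the three patterns, which is a total effect.

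The protocol itself gives reasons why some of these factors could respond to the pattern. It raises comfort and ease of use as open questions, lists discomfort as a possible risk, and says an earlier pattern saved pumping time. Comfort and time per session could alter how often a mother pumps. Low volume could prompt consultations or galactagogue use, and could affect mood or goals.

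Feed type is the clearest case. Under Aim 1, milk is weighed and then made available to the infant, so the MOM share of feeds is downstream of pumped volume. Adjusting volume for it conditions on a consequence of the outcome. In Aim 4 the same variable would be both outcome and covariate.

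**Working it through.** **1. Timing of each factor against allocation at day 6-8**

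| Factor | When recorded | Part available before allocation |
|---|---|---|
| Pumping sessions per day | Daily, 15 days | Days up to allocation |
| Skin-to-skin care | Daily, 15 days | Days up to allocation |
| Lactation support | Ongoing; outside support by monthly survey | Episodes up to allocation |
| Mood (MAACL-R) | Before maternal discharge; day 15 | First test |
| Lactation experience | Part (a) before discharge; part (b) at end of study | Part (a) |
| Feed type, including MOM share | Entry and during the 15 days | Early days only, and an Aim 4 outcome |

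Table 1 also lists true baseline covariates (parity, BMI, delivery mode, gestational age and others), which are unaffected.

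**2. Share of a 15-day record that falls after allocation**

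With randomisation on day d and the randomisation day counted, the share is (16 − d)/15: 10/15 = 67%, 9/15 = 60% and 8/15 = 53% for d = 6, 7 and 8. Without that day it is (15 − d)/15: 60%, 53% and 47%. A 15-day summary would be roughly half to two thirds post-allocation.

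**3. The plan's own power figure**

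Inputs from Sample Size Determination: 30 per arm, two-sided alpha 0.02, 300 mL, SD 350, effect size 0.84, two-sample t-test. Noncentral-t power is 80.3% at 0.84, which reproduces the stated 80%. At 300/350 = 0.857 it is 82.0%.

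**4. Illustration of adjusting for a mediator**

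The protocol gives no mediation figures, so the shares and slopes here are assumptions. Let p be the share of the 300 mL effect that runs through the factor, and b the volume explained per SD of it. Then:

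- adjusted estimate = 300 × (1 − p), which is 300, 270, 225 or 150 mL for p = 0, 10, 25 or 50%;
- residual SD = √(350² − b²), which is 342, 316 or 268 mL for b = 75, 150 or 225;
- shift in the factor between arms = 300p/b, in SDs.

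Simulated power (20,000 replicates; shift in brackets):

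| b (mL per SD) | p = 0 | 10% | 25% | 50% |
|---|---|---|---|---|
| 75 | 83% | 72% (0.4 SD) | 45% (1.0 SD) | 13% (2.0 SD) |
| 150 | 89% | 80% (0.2 SD) | 60% (0.5 SD) | 23% (1.0 SD) |
| 225 | 97% | 93% (0.13 SD) | 78% (0.33 SD) | 37% (0.67 SD) |

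The comparator is 82% unadjusted. The cells that need a shift of 1 to 2 SD deserve little weight.

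**5. Adding an unmeasured common cause**

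Assume b = 100, and a common cause that correlates 0.5 with the factor and adds 75 mL per SD to volume. The fitted slope on the factor becomes 100 + 75 × 0.5 = 137.5. With a shift of 3p, the adjusted estimate is 300 − 137.5 × 0.75 = 197 mL at p = 25%, and 300 − 137.5 × 1.5 = 94 mL at p = 50%. Simulation agreed.

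**The case against.** The strongest reply is that no faulty analysis is actually fixed. The factors are documented so that they can be included; no adjusted model or covariate set is stated, and the only between-arm test named is an unadjusted t-test. Covariate choice is commonly left to a SAP, and each daily record can be split at randomisation. The sentence also covers all enrolled mothers and directly follows Exploratory Aim 2, where randomised mothers are compared with non-randomised ones and adjustment for confounders is legitimate. Mothers are blinded to pattern, skin-to-skin care depends largely on the infant's condition, and lactation support is offered to all, so for those two factors an effect of allocation may be small. Nothing proposes adjusting Aim 4, and feed type shares a combined row with demographics. The mediation figures are assumed.

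Much of this stands, and it limits the point. It does not remove it. The protocol does not confine adjustment to Exploratory Aim 2, and it names specific post-allocation measurements as covariates, including the second mood test and the end-of-study questionnaire. That is a stated list, not a detail left open. Permission without a limit also leaves the choice to be made after the data are seen. For feed type, the timing cell expressly includes the 15-day period, so a baseline-only reading is not available.

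**Conclusion.** The point holds and should be fixed. The protocol's list of candidate adjustment variables mixes baseline characteristics with factors measured after allocation, and includes an Aim 4 outcome that is also a consequence of the primary outcome. Using those values in Aims 1, 2 or 4 would change what is estimated.

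The timing and the overlap with Aim 4 are certain from the text. The size of any harm is not: it is near zero if the pattern does not affect the factor, and grows with the share of the effect that runs through it. Power is not the main issue, since a prognostic factor that mediates only weakly may cost no power or even gain some. The existing unadjusted sample-size calculation is unaffected.

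**What to change.** Add one sentence to the Confounding Variables paragraph: the between-arm randomised comparisons (Aims 1, 2 and 4) adjust only for values fixed before the allocated pattern starts. Suitable candidates are pre-randomisation volume and sessions per day, the first MAACL-R, lactation experience part (a), and maternal and infant entry characteristics. Because randomisation falls on day 6, 7 or 8, cut the early summaries at each mother's own allocation, not at a common day.

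Remove feed type from the covariate list and keep it as an outcome. Report later pumping sessions, skin-to-skin care, lactation support, day-15 mood and lactation experience part (b) descriptively, or in analyses labelled as mediation. Adjustment for confounders in Exploratory Aim 2 can stay, without feed type.

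The cost is wording only. The baseline versions are already collected.
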